### **8.5.2 Secondary Endpoints**

The proportion of subjects who achieve an EASI-50 response (50% reduction in EASI score from baseline) at Week 2 will be compared between the treatment groups. Group proportions and the difference between these proportions will be calculated along with the corresponding 90% confidence interval. These data will also be analysed using logistic regression, including treatment and baseline. The odds ratio and accompanying 90% confidence interval will be presented.

The proportion of subjects who achieve an EASI-75 response (75% reduction in EASI) and the proportion of subjects who are responders for IGA score (reduction from baseline of at least 2 points) at Week 2, will be analysed using the same analyses described for the EASI-50 response. The changes from baseline in IGA score will also be summarized using categorical shift tables.

The changes from baseline in body surface area, pruritus NRS score for worst itch, NRS score for sleep disturbance and duration of itching at Week 2 will be analysed using the same analyses described for the primary analysis.

The changes from baseline in VRS score will be summarized using categorical shift tables.

The PGIC score will be summarized and analysed using logistic regression, presenting odds ratios and associated 90% confidence intervals for the comparison between treatment groups.

Secondary endpoints will be analysed using the Full Analysis Set.

### **8.5.3 Exploratory Endpoints**

Responses to the Ziarco ointment questionnaire will be summarized by treatment group.

## **8.6 Safety Analyses**

Safety data will be summarized by treatment group for each cohort using all subjects in the Safety Analysis Set.

No imputation will be used for handling missing data, with the exception of conservative approaches taken for missing adverse event information (e.g. intensity). Details of such conventions will be documented in the SAP prior to the study database being locked.

Adverse events will be coded using the MedDRA dictionary. The incidence of all treatment emergent adverse events will be tabulated by treatment group and by treatment group and severity. Those events regarded as possibly treatment related by the investigator will be summarized separately.

Changes from baseline in laboratory parameters, vital signs and ECG data will be summarized by visit for each treatment group.

For Cohort 1 only, local toleration assessed by the Draize score, will be summarized by visit for each treatment group. The changes from baseline in Draize score will also be summarized using categorical shift tables.

## **8.7 Pharmacokinetic Analyses**

ZPL-5212372 concentrations (all cohorts) and parameters (Cohorts 1 and 2 only) will be summarised for each cohort using all subjects in the Pharmacokinetic Set.

Individual profile and median plots will also be plotted. Median profiles for Cohorts 1 and 2 will be plotted by day.

The ZPL-5212372 pharmacokinetic parameters  $AUC_{\tau}$ ,  $AUC_{last}$  and  $t_{1/2}$  will be generated using non-compartmental methods.  $C_{max}$  and  $T_{max}$  will be determined directly from the data. Where possible, the apparent terminal elimination phase rate constant ( $k_{el}$ ) will be calculated by linear regression of the log-linear plasma concentration-time curve. Only those time points judged to describe the terminal log-linear decline will be used in the regression. The apparent terminal elimination half-life ( $t_{1/2}$ ) will be calculated as follows:

$$t_{1/2} = \ln 2 / k_{el}$$

## **8.8 Interim Analyses**

The study will have data reviews conducted between each cohort (see section 3).

## **8.9 Determination of Sample Size**

The sample sizes for Cohorts 1 and 2 are not based on formal statistical testing. Their sample sizes are considered sufficient to obtain suitable safety, tolerability and PK data prior to starting Cohort 3.

For Cohort 3 the sample size of 30 subjects has been determined on the basis of comparing the mean ZPL-5212372 Week 2 percentage change from baseline in the EASI score to that for placebo. With 20 subjects in the ZPL-5212372 group and 10 subjects in the placebo group, there is 80% power of obtaining a statistically significant result, assuming that there is an improvement of at least 30% with ZPL-5212372 compared to placebo and a standard deviation for the percentage changes from baseline between subjects of 30%. This is based on the analyses described and a 1-sided test at the 5% level of significance.

## **9 ETHICAL, LEGAL AND ADMINISTRATIVE ASPECTS**

### **9.1 Data Quality Assurance**

The Sponsor (or its delegate) will conduct a site visit to verify the qualifications of each investigator, inspect the site facilities, and inform the investigator of responsibilities and the procedures for ensuring adequate and correct documentation.

The investigator is required to prepare and maintain adequate and accurate case histories designed to record all observations and other data pertinent to the study for each study participant. All information recorded on the CRFs for this study must be consistent with the subjects' source documentation (i.e., medical records).

### **9.2 Case Report Forms and Source Documentation**

All data obtained during this study should be entered in the CRFs promptly. All source documents from which CRF entries are derived should be placed in the subject's medical records. Measurements for which source documents are usually available include laboratory assessments, and ECG recordings.

The original CRFs for each subject will be checked against source documents at the study site by the study monitor.

After review by the study monitor, completed CRFs will be marked as complete and verified. [REDACTED] Data Management will review the CRFs within the electronic data capture (EDC) system. Where data is discrepant, Data Management will raise queries for the site to resolve within the EDC.

### **9.3 Access to Source Data**

During the course of the study, a monitor will make site visits to review protocol compliance, compare CRFs and individual subject's medical records, assess drug accountability, and ensure that the study is being conducted according to pertinent regulatory requirements. CRF entries will be verified with source documentation. The review of medical records will be performed in a manner to ensure that subject confidentiality is maintained.

Checking of the CRFs for completeness and clarity, and cross-checking with source documents will be required to monitor the progress of the study. The investigator should be available at each monitoring visit to answer any queries. Moreover, regulatory authorities of certain countries, IECs, and/or the Sponsor's Clinical Quality Assurance Group may wish to carry out such source data checks and/or on-site audit inspections. Direct access to source data will be required for these inspections and audits; they will be carried out giving due consideration to data protection and medical confidentiality. The investigator assures the Sponsor of the necessary support at all times.

#### **9.4 Data Processing**

The site will be supplied with the following data collection tool: a web browser address for EDC that has been fully validated and conforms to 21CFR11 requirements. The trained investigator site staff will enter the data required by the protocol into the CRFs from source documents (e.g., medical records and study-specific data capture tools as needed) using the [REDACTED] supplied data collection tool. All information in the CRFs must be traceable to these source documents. Data recorded directly into the CRFs will be defined before study start and the CRFs will be considered the source data. Clinical Research Associates and a Data Manager will review CRFs entered by investigational staff for completeness and accuracy. Automatic quality programs check for data discrepancies in the CRFs and the resulting queries will be notified to the investigational site using an electronic data query process within the EDC. Designated investigator site staff are required to respond to queries and make any necessary changes to the data. Details of the data correction process will be specified in the Data Management Plan. After database lock, the investigator will receive a CD-ROM of the subject CRFs (PDF) for archiving at the investigational site.

A validated, electronic database will be employed from the EDC system. An audit trail of all changes to this database, including the date, reason for the data change and who made the change, will be maintained within the same database. The audit trail will be part of the archived data at the end of the study.

#### **9.5 Archiving Study Records**

Adequate records as required by ICH GCP and FDA CFR, will be maintained for the study. This will include subject medical records, investigator logs, CRFs, laboratory reports, work sheets, signed SICFs, drug dispensing records, adverse experience reports, information regarding subjects' discontinuation and electronic data. Essential documents should be retained until at least 2 years after the last approval of a marketing application in an ICH region and until there are no pending or contemplated marketing applications in an ICH region or at least 2 years have elapsed since the final discontinuation of clinical development of the investigational product. These documents should be retained for a longer period. However, if required by the applicable regulatory requirements or by an agreement with the sponsor. It is the responsibility of the sponsor to inform the investigator/institution as to when these documents no longer need to be retained.

## **9.6 Good Clinical Practice**

The procedures set out in this study protocol are designed to ensure that the Sponsor and investigator abide by the principles of the Good Clinical Practice guidelines of the International Conference on Harmonization (ICH), and of the Declaration of Helsinki (2013). The study also will be carried out in keeping with local legal requirements.

## **9.7 Confidentiality**

All study findings and documents will be regarded as confidential. The investigator and members of his/her research team must not disclose such information without prior written approval from the Sponsor.

The anonymity of participating subjects must be maintained. Subjects will be identified on CRFs and other documents submitted to [REDACTED] by their subject number and/or birth year, not by name. Documents not to be submitted to [REDACTED] that identify the subject (e.g., the signed informed consent) must be maintained in confidence by the investigator.

## **9.8 Informed Consent**

Before each subject is admitted to the study, informed consent will be obtained from the subject (or his/her legally authorized representative) according to the regulatory and legal requirements of the participating country (i.e., the Declaration of Helsinki, ICH GCP, and other applicable local regulations). This consent form must be dated and retained by the investigator as part of the study records. The investigator will not undertake any investigation specifically required only for the clinical study until valid consent has been obtained. The terms of the consent and when it was obtained must also be documented in the CRF.

If a protocol amendment is required, the informed consent form may need to be revised to reflect the changes to the protocol. If the consent form is revised, it must be reviewed and approved by the appropriate IEC, and signed by all subjects subsequently enrolled in the study as well as those currently enrolled in the study.

## **9.9 Protocol Approval and Amendment**

Before the start of the study, the study protocol and/or other relevant documents will be approved by the IEC/Competent Authorities, in accordance with local legal requirements. The Sponsor must ensure that all ethical and legal requirements have been met before the first subject is enrolled in the study.

This protocol is to be followed exactly. To alter the protocol, amendments must be written, receive approval from the appropriate personnel, and receive IEC/Competent Authority approval prior to implementation (if appropriate). Administrative changes (not affecting the subject benefit/risk ratio) may be made without the need for a formal amendment. All amendments will be distributed to all protocol recipients, with appropriate instructions.

### **9.10 Duration of the Study**

The planned duration of the study for each subject will be approximately 6 to 8 weeks (assuming 4 weeks screening, 1-2 weeks treatment [Cohort 1 and 2: 1 week of treatment or Cohort 3: 2 weeks of treatment] and 1-2 weeks follow-up). The study will close when all subjects have completed the final follow-up visit.

### **9.11 Premature Termination of the Study**

If the investigator or the Sponsor becomes aware of conditions or events that suggest a possible hazard to subjects if the study continues, the study may be terminated after appropriate consultation between the relevant parties. The study may also be terminated early at the Sponsor's discretion in the absence of such a finding.

Conditions that may warrant termination include, but are not limited to:

- The discovery of an unexpected, significant, or unacceptable risk to the subjects enrolled in the study;
- Failure to enroll subjects at an acceptable rate;
- A decision on the part of the Sponsor to suspend or discontinue development of the drug.

### **9.12 Liability and Insurance**

The Sponsor will take out reasonable third-party liability insurance cover in accordance with all local legal requirements. The civil liability of the investigator, the persons instructed by him and the hospital, practice or institute in which they are employed and the liability of the Sponsor with respect to financial loss due to personal injury and other damage that may arise as a result of the carrying out of this study are governed by the applicable law.

The Sponsor will arrange for subjects participating in this study to be insured against financial loss due to personal injury caused by the pharmaceutical products being tested or by medical steps taken in the course of the study.

### **9.13 Publication Policy**

By signing the study protocol, the investigator agrees with the use of results of the study for the purposes of national and international registration, publication and information for medical and pharmaceutical professionals. If necessary, the authorities will be notified of the investigator's name, address, qualifications and extent of involvement.

After study completion, data from the entire study will be considered for reporting at a scientific meeting and for publication in a scientific journal. Ziarco will coordinate these activities and will work with the Principal Investigator to determine how the manuscript is written and edited, the number and order of authors, the publication to which it will be submitted and other related issues. Authorship will be based on criteria stipulated by leading clinical journals (e.g. contribution to one or more areas of study design, data analysis and interpretation, manuscript preparation and review, etc.).

An investigator shall not publish any data (poster, abstract, paper, etc.) without having consulted with the Sponsor in advance.

## 11 APPENDICES

---

**APPENDIX 1 – CRITERIA FOR SAFETY VALUES OF POTENTIAL  
CLINICAL CONCERN****Haematology**

Hemoglobin	<0.8 x baseline
Hematocrit	<0.8 x baseline
WBC	<2.5 or >17.5 x 10  /mm 
Platelets	<75 or >700 x 10  /mm 

**Chemistry**

Total bilirubin	>1.5 times the upper limit of the reference range
AST	>3 times upper limit of the reference range
ALT	>3 times upper limit of the reference range
GGT	>3 times upper limit of the reference range
Alk Phosphatase	>3 times upper limit of the reference range
Creatinine	>1.3 times upper limit of the reference range
Urea	>1.3 times upper limit of the reference range
Glucose, fasting	<0.6 or >1.5 times the limits of the reference range
Uric acid	>1.2 times upper limit of the reference range
Sodium	<0.95 or >1.05 times the limits of the reference range
Potassium	<0.9 or >1.1 times the limits of the reference range
Calcium	<0.9 or >1.1 times the limits of the reference range
Albumin	<0.8 or >1.2 times the limits of the reference range
Total protein	<0.8 or >1.2 times the limits of the reference range

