- 13 Patients who have evidence of significant concomitant clinical disease that could interfere with the conduct or safety of this study, based upon a complete medical history, full physical examination, and a 12-lead resting ECG and laboratory safety tests. For example the presence of any other acute and/or unstable clinical disease, other than AD, such as:
- Poorly controlled Type I or Type II diabetes.
  - Seizure disorder or epilepsy.
  - Cerebrovascular accident.
  - Active or latent infection (eg, hepatitis).
  - Cancer (other than cutaneous basal cell) in the last 5 years.
  - Congestive heart failure.
  - Coronary artery disease.
  - Renal insufficiency and/or serum creatinine  $>1.5$  X upper limit of normal (ULN). Subjects with serum Creatinine  $<2$  X ULN may be retested once.
  - A major surgical operation during the 30 days prior to screening.

Stable well-controlled chronic conditions such as controlled hypertension [excluding those on  $\beta$ -blockers, calcium channel blockers (Class I or II)], thyroid disease, well-controlled Type 1 or Type 2 diabetes, hypercholesterolemia, gastroesophageal reflux, or depression under control with medication (other than tricyclic antidepressants), are acceptable provided the symptoms and medications would not be predicted to compromise safety or interfere with the tests and interpretations of this study.

- 14 Clinically significant cardiac disease or ECG abnormalities, including:
- Predominant heart rhythm other than normal sinus rhythm
  - AV block greater than first degree
  - Resting pulse rate  $>100$  or  $<50$  bpm
  - Electrocardiographic evidence or a history of myocardial infarction
  - Electrocardiographic evidence of conduction system abnormality
  - Subjects with pre-randomisation evidence of QTc prolongation (defined as  $>450$  msec).

The PI should decide whether ECG abnormalities other than those listed are clinically significant and should exclude the subject from enrolment.

- 15 Patients with a personal or family history of prolonged QTc interval.
- 16 Clinically significant liver function tests (LFTs; AST, ALT, total Bilirubin) Subjects with LFTs  $>1.5$  X ULN and  $<2$  X ULN may be retested once.
- 17 Positive HIV, HBsAg and HBcAb result or positive anti-hepatitis C virus serology (as determined by multi-antigen EIA)
- 18 Pregnant and nursing females.

- 19 Donation or intent to donate blood, or blood components during the study or within one month after completion of the study.

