## 7.16 Safety

### 7.16.1 Adverse Events

#### 7.16.1.1 Definitions

An AE (or adverse event) is any untoward medical event that occurs in a subject and does not necessarily have a causal relationship with study treatment. An AE can therefore be any unfavorable and unintended sign (including an abnormal laboratory finding), symptom, or disease temporally associated with the use of an investigational product, whether or not related to the product.

A treatment-emergent AE will be defined as an AE that begins or that worsens in severity after at least one dose of study drug (ZPL-5212372 or placebo ointment) has been administered.

An adverse drug reaction (ADR) is any untoward and unintended response in a subject to an investigational medicinal product which is related to any dose administered to that subject.

An unexpected adverse reaction is an adverse reaction the nature and severity of which is not consistent with the information about the medicinal product in the Investigator's Brochure.

All AEs, including intercurrent illnesses, occurring during the study will be documented in the CRF. Concomitant illnesses, which existed prior to entry into the study, will not be considered AEs unless they worsen during the treatment period. Pre-existing conditions will be recorded in the CRF as Medical History.

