**Vital Signs**

Pulse Rate	Supine/Sitting: <40 or >120 bpm    Erect: <40 or >140 bpm
Blood Pressure	Systolic ≥30 mm Hg change from baseline in same posture Systolic <90 mm Hg Diastolic ≥20 mm Hg change from baseline in same posture Diastolic <50 mm Hg

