#### 10.4. LABORATORY EVALUATIONS

The change from baseline and percentage change from baseline in haematology, chemistry, and continuous urinalysis parameters will be summarised by treatment group using descriptive statistics. Discrete urinalysis parameters will be summarised with counts and percentages by treatment group. The number of normal and abnormal (low and high) records will also be summarised with counts and percentages by treatment group. Baseline and all protocol specified on treatment (i.e. on or before the date of last study medication plus 1) visit data will be summarised. If a baseline value is missing for a parameter, the screening value will be used as the baseline value.

Subjects who satisfy the criteria for values of potential clinical concern will be summarised and listed separately. The summary will present the number of subjects with at least one ontreatment visit value (including unscheduled visits) satisfying the criteria. The listing will include all data for the subject and parameter which satisfied the criteria. The record satisfying the criteria will be identified on the listing. The criteria are:

SAP Version v2.0 Page 34 of 43

Date: 16th March 2017

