**Table 3: Criteria for Vital Signs** 

Parameter	Category	Criteria
Systolic BP	1	< 90 mmHg*
Systolic br		≥ 90 mmHg
	2	< 30 mmHg change from baseline
		≥ 30 mmHg change from baseline*
Diastolic BP	1	< 50 mmHg*
Diastolic br		≥ 50 mmHg
	2	< 20 mmHg change from baseline
		≥ 20 mmHg change from baseline*
Pulse	1	< 40 bpm*
ruise		≥ 40 - ≤120 bpm
		> 120 bpm*
	2	< 40 bpm and at least one value > 120 bpm
		< 40 bpm and no value > 120 bpm
		≥ 40 bpm

\* Indicates criteria to be identified in listing.

Vital signs data will be listed. The listing will include actual sampling times and deviations from nominal sampling times. The listing will flag records that satisfy the above criteria.

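### For the absolute laboratory limits and the low blood-pressure limits, the on-treatment concern counts in SAP 10.4 and 10.5 do not separate values already beyond the limit before the first application from new ones

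*Protocol*

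**What the plan says.** Protocol Appendix 1 and SAP Tables 2 and 3 mix two kinds of criterion.

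- **Relative to baseline.** Haemoglobin and haematocrit use "<0.8 x baseline". Blood pressure has "Systolic ≥30 mm Hg change from baseline in same posture" and "Diastolic ≥20 mm Hg change from baseline in same posture", carried into SAP Table 3 as "≥ 30 mmHg change from baseline" for systolic, with a parallel 20 mmHg row for diastolic.
- **Absolute.** White cells, platelets, all chemistry parameters and urine cells have fixed limits; creatinine and urea, for example, use ">1.3 times upper limit of the reference range". Systolic below 90, diastolic below 50, and pulse below 40 or above 120 bpm are also absolute.

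The counting rule is in the SAP. Section 10.4 reports subjects with at least one on-treatment "visit value (including unscheduled visits) satisfying the criteria". The text after Table 2 counts ALT, AST, alkaline phosphatase and total bilirubin the same way at >1.5, >2 and >3 x ULN. Section 10.5 places each subject's on-treatment maximum and minimum into the Table 3 categories. None of these rules refers to whether the limit was already met before dosing.

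The adverse event rule in Protocol 7.16.1.1 does: "A treatment-emergent AE will be defined as an AE that begins or that worsens in severity after at least one dose of study drug".

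**The concern.** A subject who is beyond an absolute limit on Day 1 and stays at the same value appears in the table exactly like a subject who crossed the limit on treatment. The table cannot tell a reader which is which.

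Safety is the primary objective of Cohorts 1 and 2 and a secondary objective of Cohort 3. The arms are very small, so a chance imbalance of one or two pre-existing values can dominate the comparison of active with placebo on these tables. The plan already separates old from new for adverse events, and it gives IGA and VRS shift tables, but its table index has no laboratory shift table.

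**Working it through.** The plan states no figure for this point, so there is nothing to reproduce. The check has four steps.

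**1. How many criteria are affected.**
- SAP Table 2 has 4 haematology + 10 chemistry + 2 urinalysis = 16 parameters. Two (haemoglobin, haematocrit) are relative to baseline, leaving 16 − 2 = 14 absolute.
- Adding the 4 separately counted liver tests gives 14 + 4 = 18 absolute of 20.
- SAP Table 3 stars 6 vital-sign criteria: 2 are changes from baseline and 4 are absolute. Two of those 4 are pulse limits.

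**2. Whether the entry rules allow a subject to start beyond a limit.**
- *Creatinine, Cohorts 2 and 3.* The example in Protocol 4.4 excludes above 1.5 x ULN, and the concern limit is 1.3 x ULN. A patient between the two is not excluded by that example and meets the criterion on entry.
- *Liver tests.* Protocol 4.3 excludes clinically significant results above 1.5 x ULN in Cohort 1. The Cohort 2 and 3 criterion, in the text available, gives only a retest range. The SAP counts from above 1.5 x ULN.
- *Glucose.* Protocol 4.4 accepts "well-controlled Type 1 or Type 2 diabetes", subject to conditions, and the concern limit is absolute.
- *GGT, alkaline phosphatase, urea, uric acid, white cells, platelets, blood pressure.* No numerical entry limit is given.
- *Pulse.* Entry excludes below 50 and above 100 bpm in every cohort. This lies inside the 40 and 120 bpm limits, so a pre-existing breach is largely prevented.

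**3. Effect of one such subject.** The allocation is 2:1, giving 20 v 10 in Cohort 3 and 8 v 4 in a cohort of 12.
- Cohort 3: 1/20 = 5 points on active; 1/10 = 10 points on placebo.
- Cohort of 12: 1/8 = 12.5 points on active; 1/4 = 25 points on placebo.

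**4. Chance imbalance in Cohort 3.** Let q be the share of subjects who meet an absolute limit both before dosing and on treatment. The documents give no value, so q is assumed and shown over a range. The SD of the difference in arm rates from this source alone is sqrt(q(1 − q)(1/20 + 1/10)) = sqrt(0.15 q(1 − q)). The chance of at least one such subject among 30 is 1 − (1 − q)^30.

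| Assumed q | Expected of 30 | Chance of at least one | SD of rate difference |
|---|---|---|---|
| 1% | 0.3 | 26% | 3.9 points |
| 2% | 0.6 | 45% | 5.4 points |
| 5% | 1.5 | 79% | 8.4 points |
| 10% | 3.0 | 96% | 11.6 points |

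**The case against.** The strongest reply is that the missing information is mostly available elsewhere. SAP 10.4 summarises change from baseline by arm and tabulates low and high values at baseline as well as on treatment. The concern listing shows all of the subject's data for the flagged parameter. With at most 30 subjects in a cohort, a reader can check each case. This limits the consequence but does not remove the gap. The low/high counts use the reference limits, not the concern limits. Mean changes do not show who was already beyond a limit. The listing leaves the reader to recount the table by hand.

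The reply is also right that eligibility judgement lowers the frequency. Cohort 1 subjects must have no clinically relevant abnormality. Protocol 4.4 excludes significant concomitant disease and laboratory abnormalities that could affect risk or interpretation, and it accepts diabetes only if it would not interfere with the tests. The 12.5 and 25 point figures therefore show what one case would do; they do not say that a case is likely, least of all in Cohort 1.

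Four stronger readings are tempting, and the documents do not support them.
- *That none of the concern counts looks at baseline.* Haemoglobin, haematocrit and both blood-pressure change criteria do.
- *That a value seen only before dosing is counted.* SAP 6.1 defines on-treatment by an upper date limit alone, but it applies the term to post-baseline visits, and 10.4 names baseline separately. Read in context, the limit must be met again on treatment. A literal program that includes unscheduled values could still pick up pre-dose retests, so the wording should be closed.
- *That the comparison is biased.* Allocation is randomised, so this is noise. The counts are descriptive, and no testing is planned in Cohorts 1 and 2.
- *That subjects beyond a limit at baseline should be left out of the count.* A patient moving from 1.35 to 2.5 x ULN would then disappear, whereas the adverse event rule keeps worsening.

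**Conclusion.** The point holds for the absolute limits: 14 of the 16 Table 2 parameters, the four liver tests, systolic below 90 and diastolic below 50. Unchanged pre-existing values and new values share one count. The clearest documented route is creatinine between 1.3 and 1.5 x ULN in Cohorts 2 and 3. For the other analytes and blood pressure, the route is the absence of a firm numerical entry limit, tempered by clinical judgement.

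One subject is worth 5 or 10 points in Cohort 3 and 12.5 or 25 points in a cohort of 8 v 4; these figures follow from the planned arm sizes. The SD of about 4, 5, 8 or 12 points in Cohort 3 rests on an assumed prevalence of 1%, 2%, 5% or 10%, pooled over limits, and the documents support no single value.

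This is a presentational gap in descriptive safety tables. It affects neither the efficacy analysis nor any test. It is worth closing because the change loses no cases, uses data already collected and makes the comparison between very small arms easier to read.

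**What to change.** Amend SAP 10.4 and 10.5. Appendix 1 only sets the thresholds and can stay as it is.

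1. Keep the existing count of subjects with any on-treatment value meeting the criterion.
2. For the absolute Table 2 criteria, the liver counts, and the systolic <90 and diastolic <50 categories, add two columns by arm: criterion already met at baseline, and newly met after the first application. Use the SAP's existing baseline definition, including the screening value where baseline is missing.
3. Among subjects who met the criterion at baseline, identify those who worsened on treatment, for example by moving to a higher liver-test multiple or further beyond the limit. Do not drop them from any count.
4. State that on-treatment values are those recorded after the first application, up to the existing end date.
5. Keep all listings.

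The cost is a few sentences and extra columns in the potential-concern tables for haematology, chemistry, liver tests and urinalysis, and in the categorical vital-signs table. No new data are needed. In Cohort 3 the only scheduled on-treatment laboratory sample is Day 15, so the comparison with baseline is simple.
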